9.3.2 Patient related assessments

9.3.2.1 Demography

The following demographic parameters will be recorded at the Visit 1:

- Month and year of birth (in countries where this is not allowed only year of birth).
- Ethnic background (if allowed in the specific country, NA for France).
- Sex.

9.3.2.2 Bleeding treatment history and history of bleeding episodes

- Current prophylactic treatment and treatment for the last five years. If shorter, for the actual prophylactic period (name of product, dose, dose frequency and duration of prophylaxis (start/stop date)).
- Number of bleeds during prophylaxis treatment in the last 24 months (both treatment required and non-treatment requiring).
- On-demand treatment as reported by the patient.
- Number of treatment requiring bleeding episodes within the last 24 months.
- FXIII product used, and product used for the last five years. If shorter, for the actual ondemand period (name and yearly dose, if available).
- Surgeries within the last 12 months.
- Date of surgery.
- Type of surgery (minor/major and elective/emergency).
- Haemostatic product (name if available and dose).

9.3.2.3 Pre-defined complications

At the Visit 1 it will be recorded if the patient has been diagnosed with any of the following predefined complications:

- Coagulation disorders (other than congenital FXIII A-subunit deficiency).
- Allergic reactions to pharmaceutical drug.
- History of embolic or thrombotic events.
- Lack of therapeutic effect of FXIII containing products.

9.3.2.4 Medical history/concomitant illness

Details on medical history and concomitant illnesses will be recorded at the Visit 1 during a medical interview and review of relevant medical records.

02 February 2016 | Novo Nordisk Protocol Date: 2.0

Final

Study ID: NN1841-3868 Version: CONFIDENTIAL UTN: U1111-1131-1558 Status: EU PAS No.: ENCEPP/SDPP/3687 Page: 33 of 65

All concomitant illnesses must be recorded at study entry, including any recent chronic infectious diseases (in the last 6 months). During the study period any change in concomitant illnesses will be recorded until end of study visit (see section 9.3.2.7).

9.3.2.5 **Details on diagnosis of FXIII CD**

Diagnosis of FXIII deficiency as evidenced in the patient's medical records

- Date of diagnosis.
- Underlying gene defect, if known (FXIII subunit A, FXIII subunit B, other).
 - Genotyping been performed.
 - Mutation been identified (mutation no.).
 - Type of mutation (substitution (missense, nonsense, splice site), deletion, insertion, duplication, inversion, translocation, other).
 - Description of the sequence variant (DNA level, Protein level).
- Type of disorder (FXIII heterozygous, homozygous, other).
- FXIII activity level at time of diagnosis.
- Current FXIII activity level, if available.
- History of anti-FXIII antibodies.

Nature of any antibodies detected in the past:

- Neutralising.
- Non-neutralising.

If any antibodies detected in the past:

- Most recent antibody value.
- Date of most recent antibody value.
- Date of first finding of antibodies.
- Historical maximum antibody value.

Family history (1st degree relatives, other relatives):

- History of antibodies toward FXIII
- Congenital haemostatic disorder (FXIII deficiency (heterozygous, homozygous) and other).
- Congenital pro-thrombotic disorders (FZ Leiden (G1691A), Prothrombin mutation (G20210A), Protein C deficiency, Protein S deficiency, Anti-thrombin deficiency, other.

9.3.2.6 **Concomitant medication**

Definition of concomitant medication: any medication other than rFXIII that is taken during the study, including reported at Visit 1

Details of all concomitant medication must be recorded at study entry (i.e., at the first visit, Visit 1), including any recent vaccinations (in the last 6 months). Any changes in medication must be recorded at each visit (assessment visits and end of study visit) in the CRF.

Protocol Date: 02 February 2016 Novo Nordisk Study ID: NN1841-3868 Version: 2.0

UTN: U1111-1131-1558

EU PAS No.: ENCEPP/SDPP/3687

CONFIDENTIAL

Status: Final
Page: 34 of 65

9.3.2.7 Concomitant illnesses

Definition of concomitant illness: any illness that is present at the start of the study (i.e. Visit 1).

Details of all concomitant illness must be recorded in the baseline CRF. The information collected for concomitant illness should include diagnosis, date of onset, date of resolution or continuation. A clinically significant worsening of a concomitant illness must be reported as an AE. If the change influences the patient's eligibility to continue in the study, the sponsor must be informed.

9.3.2.8 Body measurements

The following must be recorded in the patient's record and the CRF, if available or performed:

- Height (cm or inches) without shoes will be measured at the Visit 1.
- Body weight (kg or lbs) will be recorded with standardised scale (patient in light clothing and without shoes) at the Visit 1, the assessment visits and end of study visit.

9.3.2.9 Vital signs

The following must be recorded in the patient's record and the CRF, if available or performed:

Standard safety-related vital signs will be recorded at the Visit 1 and at the end of study visit:

- Pulse.
- Blood pressure (systolic and diastolic blood pressure).

Blood pressure and pulse rate should preferably be measured using an automatic device; after the patient has rested comfortably for 3 minutes. Measurements will be reported in the CRF.

9.3.3 Assessments for safety

Safety information must be collected during each contact (visit or telephone, excluding Visit 1 and safety visits, where the patient is not seeing the Physician or his staff e.g., visits to the laboratory) with the Physician or study site staff. This may be done by posing a simple question such as "have you experienced any problems since the last contact?" For definitions on safety information collected in this study see section 11.2.

After the first administration of rFXIII following enrolment in the study all adverse drug reactions, serious adverse events and medical events of special interest must be collected and reported according to section 11.3.

 Study ID: NN1841-3868
 CONFIDENTIAL
 Version:
 2.0

 UTN: U1111-1131-1558
 Status:
 Final

 EU PAS No.: ENCEPP/SDPP/3687
 Page:
 35 of 65

9.3.3.1 Specific adverse drug reactions events

In this study the incidence of specific adverse drug reactions and events are of special interest: anti-FXIII antibody, allergic reactions, embolic and thrombotic events, lack of effect. For definitions, see section 9.3.3.1.

Anti-FXIII antibodies

Detection of anti-FXIII antibodies (see section 9.3.3.2) in blood samples. Both FXIII non-neutralising and FXIII neutralising antibodies are considered to be medical events of special interest, and are to be reported as such (see section 11.2.4).

Allergic reaction

An allergic reaction is any acute or delayed type hypersensitivity reaction (clinical signs may include tightness of the chest, hypotension, anaphylaxis or various types of skin rashes), and is to be reported as a medical event of special interest (see section 11.2.4).

Embolic and thrombotic events

Any myocardial infarction, pulmonary embolism, cerebral thrombosis or infarction, and other significant embolic or thrombotic events, including visceral arterial embolus or thrombus, extremity arterial embolus or thrombus, portal venous thrombosis or deep venous thrombosis of extremity veins, are embolic and/or thrombotic events, and are to be reported as a medical event of special interest (see section 11.2.4). Superficial thrombophlebitis is not considered an embolic and thrombotic event.

Lack of therapeutic effect

In the case of suspected decrease or lack of therapeutic effect, including FXIII activities that fail to reach expected levels, analysis for antibodies should be performed (see section 9.3.3.2). Any suspicion of a lack of expected therapeutic effect is to be reported as a Medical event of special interest (see section 11.2.4).

9.3.3.2 Blood sampling

Blood samples collected in this study are samples taken as part of routine treatment established by the Physician as follows:

- Anti-FXIII antibody (see section 9.3.3.2).
- FXIII activity (optional) (see section 9.3.3.2).
- Blood samples for anti-FXIII antibody assessment should be taken, at Visit 1 and at a visit to be conducted 1 year after the patient entry into the study for patients consenting to testing in countries where the collection of blood samples for anti-FXIII antibody assessment is possible within the confines of a non-interventional study (see section 9.3.3.2).

Protocol	Date:	02 February 2016	Novo Nordisk

 Study ID: NN1841-3868
 CONFIDENTIAL
 Version: 2.0

 UTN: U1111-1131-1558
 Status: Final Page: 36 of 65

The Physician is strongly encouraged to draw blood samples for FXIII activity and anti-FXIII antibodies if any indication of lack of therapeutic effect emerges.

Data collection should happen in conjunction with all otherwise scheduled visits to the clinic. Time and date of collection should be recorded in the CRF.

Blood samples for anti-FXIII antibodies (Central laboratory)

When judged necessary by the treating Physician, blood samples will be drawn for analysis of anti-FXIII antibodies prior to any planned rFXIII injection.

Sample for antibody analysis may be taken at any visit.

Additionally, samples for antibody analysis should be taken, at Visit 1 and at a visit to be conducted 1 year after entry of the patient into the study, for patients consenting to testing, in countries where the collection of blood samples for anti-FXIII antibody assessment is possible within the confines of a non-interventional study.

When lack of therapeutic effect is indicated by bleeding or laboratory findings, the Physician is strongly encouraged to sample for anti-FXIII antibody detection as this is part of normal practice.

The antibody assessment is a stepwise tiered process involving detection of anti-rXIII binding antibodies (antibody specificity, titer, isotyping) and evaluation of neutralising antibody capacity. Analytical protocols (both ELISA protocol and activity based assay) have been validated. Simultaneously and as supplement to the antibody assessment, one sample will be subjected to activity analysis (see below). If specific rFXIII antibodies (anti-FXIII) are detected at any time it is highly recommended that a confirmatory sample is drawn and analysed, and if confirmed, that monitoring is continued according to clinical practice.

All positive anti-FXIII antibodies should be reported as a medical event of special interest (see section 11.2.4).

The results of anti-FXIII antibodies will be reported according to section 9.6.2.2.

Central laboratory assessments

Laboratory analysis and reporting will be performed by a central laboratory designated by Novo Nordisk. Laboratory data from the central laboratories will be reported to the site and Novo Nordisk. Laboratory data will be reported to Novo Nordisk with an identifier in a manner that anonymity of patients will be maintained. All central laboratory analyses will be paid for by the sponsor.

Protocol	Date:	02 February 2016	Novo Nordisk
Study ID: NN1841-3868	Version:	2.0	

Final

CONFIDENTIAL UTN: U1111-1131-1558 Status: EU PAS No.: ENCEPP/SDPP/3687 Page: 37 of 65

The quality control of the central laboratory test results will be performed according to the regulations and specifications set by the authorities at the location of the central laboratory used for this study.

Laboratory kits with tubes will be provided to the sites for the collection of blood samples.

Volume of blood for FXIII antibody

Evaluation of anti-FXIII antibodies requires approximately 2 mL blood.

Blood samples for FXIII activity (Central laboratory)

When judged necessary by the treating Physician, blood sampling will be drawn for analysis of FXIII activity prior to any planned rFXIII injection.

FXIII activity test at Visit 1 is made to characterise the patient population at initiation. Samples for FXIII activity may be taken at Visit 1 and any assessments visit (with recommended one to six months interval depending on usual practice, unscheduled visit and end of study visit).

As routine practice or when lack of the rapeutic effect is indicated by bleeding or laboratory findings, including FXIII activities that fail to reach expected levels, the Physicians are strongly encouraged to sample for anti-FXIII antibody assessment as this is part of normal practice.

An optional analysis for FXIII activity at Visit 1 can be performed at the central laboratory. In case a blood sample at a further visit (after Visit 1) is taken for central laboratory analysis of anti-FXIII antibodies, a FXIII activity analysis is part of the antibody analysis (see section 9.3.3.2). The result of this FXIII activity analysis will be reported to the investigator together with the anti-FXIII antibody result.

If additional activity measurements are indicated these could be performed at local laboratories and reported in the CRF. Results from the central laboratory will overrule any local FXIII activity results obtained at local laboratories at the same time point.

The FXIII activity assay used at the central laboratory is the Berichrom ® assay. The assay is validated for analysis of human EDTA plasma and requires approximately 2 ml whole blood (1 ml EDTA plasma).

The results of FXIII activity in case of antibodies will be reported according to section 9.6.2.2.

Local laboratory assessment of FXIII activity

Since this is a non-interventional study; any procedures ordered by the Physician during this study will be the ones accepted as appropriate, to provide the best care for the patient at his/her discretion. If additional FXIII activity measurements are performed at local laboratories, the results should be reported in the CRF. This was requested by the Committee for Medicinal Products for Human Use

Protocol	Date:	02 February 2016	Novo Nordisk
			l .

 Study ID: NN1841-3868
 CONFIDENTIAL
 Version:
 2.0

 UTN: U1111-1131-1558
 Status:
 Final

 EU PAS No.: ENCEPP/SDPP/3687
 Page:
 38 of 65

(CHMP) in their Day 180 List of Outstanding Issues for Clinical Aspects (dated 19 April 2012). Information on the used method will be captured in the CRF..

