8.1 Objectives

8.1.1 Primary objective

The aim of this non-interventional study is to investigate the incidence of specific adverse drug reactions associated with the use of recombinant factor XIII (rFXIII) in patients with congenital FXIII A-subunit deficiency, comprising anti-FXIII antibodies, allergic reactions, embolic and thrombotic events and lack of therapeutic effect.

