8.2 Endpoints

8.2.1 Primary endpoint

Adverse drug reactions in patients with congenital FXIII A-subunit deficiency treated with rFXIII, comprising anti-FXIII antibodies, allergic reactions, embolic and thrombotic events and lack of effect, collected during study period up to 6 years.

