9.2.6 Flow chart

Table 9-1 Flow chart

Study periods		Assessment visits	End of study visit
Study periods	Visit 1	(visit 2.1, 2.2, 2.3)	(visit 3)
Vinit tour		In conjunction with	
Visit type	Visit 1	regular visit to clinic	
		Visits with	
Visit window/days	Day 0	recommended 1-6 months interval.	
PATIENT RELATED ASSESSMENTS			
Informed consent	X		
In/exclusion criteria	X		
Withdrawal criteria		X	
Demography	X		
Bleeding treatment history/history of bleeding episodes	X		
Pre-defined complications	X		
Medical history/concomitant illness	X		
Details of diagnosis of FXIII deficiency (FXIII activity and anti-FXIII antibodies)	X		
Concomitant medication	X	X	X
Concomitant illness		X	X
Body measurements	X	X^2	X^2
Vital signs	X		X
Participation in registries	X	X	X
SAFETY ASSESSMENTS			
Adverse drug reaction assessment		X	X
Specific adverse drug reaction assessment			
Blood samples for anti-FXIII antibodies ¹	X^4	X^4	X^3
Embolic and thrombotic events		X	X
Lack of therapeutic effect		X	X
Allergic reactions		X	X
Optional blood samples for FXIII activity ¹	X^3	X^3	X^3
Serious adverse event		X	X
Medical event of special interest		X	X
Medication errors and near medication errors		X	X

Protocol	Date:	02 February 2016	Novo Nordisk
		, , ,	1

 Study ID: NN1841-3868
 CONFIDENTIAL
 Version: 2.0

 UTN: U1111-1131-1558
 Status: Final Page: 27 of 65

BLEEDING ASSESSMENTS			
Bleeding episode description		X	X
Bleeding episodes since last visit		X	X
OTHER ASSESSMENTS			
Diary (instruction/evaluation)	X	X	X
 Prophylactic treatment regimes 			
 Bleeding episode description 			
 Prophylactic treatment related to surgery 			
Documentation of pregnancy		X	X

Footer	Description
1	Blood samples to be drawn prior to any planned rFXIII injection
2	Body weight only
3	Performed as part of routine clinical care established by the Physician, or in case of lack of therapeutic effect and tested simultaneously when a blood sample for anti-FXIII antibodies is collected at a visit after Visit 1 for patients consenting to testing.
4	At Visit 1 and at a visit to be conducted 1 year after entry of the patient into the study for patients consenting to testing. Performed where the collection of blood samples for anti-FXIII antibody assessment is possible within the confines of a non-interventional study. May also be collected at any visit as part of routine clinical care established by the Physician, or in case of lack of therapeutic effect.

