9.3.1.3 End of study visit (visit 3)

The end of study visit will be performed 6 years after FPFV in the study. The patients' next visit to the clinic will be defined as their end of study visit, provided they have either a minimum of 2 years participation or 24 exposure days (whichever comes first, unless the patient has dropped out).

If the Physician finds it clinically relevant sampling for anti-FXIII antibodies and FXIII activity can be performed, as part of the treatment schedule established by the Physician and when clinical suspicion of lack of therapeutic effect emerges.

The following will be observed at the end of study visit:

- Assessment of treatment of bleeding episodes since last visit:
 - Review of each bleeding episode since last visit (please refer to section 9.3.4.1).
 - Assessment of ineffective treatment episodes, if identified (please refer to section 9.3.3.2).
- Prophylactic treatment regimen (please refer to section 9.3.5.1).
- Prophylactic treatment related to surgery (please refer to section 9.3.4.2).
- Adverse drug reaction assessment (please refer to section 9.3.3).
- Specific adverse drug reaction assessment (please refer to section 9.3.3.1).
- Optional blood sample for anti-FXIII antibodies, if obtained (please refer to 9.3.3.1 section and 9.3.3.2).
- Allergic reactions (please refer to section 9.3.3.1).
- Embolic and thrombotic (please refer to section 9.3.3.1).
- Lack of the rapeutic effect (please refer to section 9.3.3.1).
- Assessments of serious adverse events (please refer to section 9.3.3).
- Medical events of special interest (please refer to section 9.3.3)
- Optional blood sample for FXIII activity, if obtained (please refer to section 9.3.3.2).
- Assessment of medication error.
- Assessment of the use of rFXIII in patients with congenital FXIII A subunit deficiency, other than for prophylactic use.
- Concomitant medication assessment (please refer to section 9.3.2.6).
- Concomitant illness assessment (please refer to section 9.3.2.7).
- Body weight measurement (please refer to section 9.3.2.8).
- Vital signs (please refer to section 9.3.2.9).
- Diary (evaluation), (please refer to section 9.3.5.1).

Protocol Date: 02 February 2016 Novo Nordisk Study ID: NN1841-3868 Version: 2.0

Status:

Page:

Final

32 of 65

Study ID: NN1841-3868 UTN: U1111-1131-1558 EU PAS No.: ENCEPP/SDPP/3687

• Documentation of pregnancy (please refer to section 9.3.5.2).

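### Antibodies count toward the primary endpoint over up to 6 years, but fixed antibody samples stop at year 1, so the planned percentage should not be read as a 6-year antibody incidence

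*Protocol*

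**What the plan says.** **Endpoint.** Section 8.1.1 sets out to "investigate the incidence of specific adverse drug reactions associated with the use of recombinant factor XIII", and anti-FXIII antibodies come first among the four kinds named. Section 8.2.1 gives the window for the whole composite: "lack of effect, collected during study period up to 6 years". Under section 9.3.3.1 an antibody event is an antibody found in a blood sample, and both kinds count: "Both FXIII non-neutralising and FXIII neutralising antibodies are considered to be medical events of special interest". Section 9.7.2.1 plans patient counts and percentages from the first study activity after consent to the end of participation. Section 9.7.2 bases every analysis on the Full Analysis Set, which section 9.7.1 defines without reference to antibody sampling.

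**Fixed samples.** Section 9.3.3.2 states that "samples for antibody analysis should be taken, at Visit 1 and at a visit to be conducted 1 year after entry of the patient", limited to consenting patients in countries where a non-interventional study may do this.

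**Other samples.** Footnote 4 of the flow chart (section 9.2.6) adds: "May also be collected at any visit as part of routine clinical care established by the Physician, or in case of lack of therapeutic effect". At visit 3 the flow chart switches to footnote 3, which covers routine care or lack of effect. Section 9.3.1.3 lists "Optional blood sample for anti-FXIII antibodies, if obtained" and says "If the Physician finds it clinically relevant sampling for anti-FXIII antibodies and FXIII activity can be performed".

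**Encouragement.** Section 9.3 encourages physicians to sample for antibodies at Visit 1, the assessment visits and the end-of-study visit. Section 9.3.3.2 allows a sample at any visit. It strongly encourages one either routinely or when bleeding or laboratory results, including FXIII activity below the expected level, point to lack of effect.

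**The concern.** The antibody component differs from the other three. Allergic reactions, thrombotic events and lack of effect can come to light when the patient is asked about problems at each contact (section 9.3.3). An antibody is an event only if blood is drawn and tested. The numerator therefore depends on the sampling schedule, while the planned percentage covers full participation in all analysed patients, whether or not they were sampled late.

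After year 1 the named prompts for a sample are suspected lack of effect, low FXIII activity and the physician's own routine. An antibody that produces neither of the first two depends on the third alone. A late count of zero could mean that no antibodies arose or that few patients were tested, and the planned table would not tell these apart. The stake is what may be said about late immunogenicity in a study meant to extend the long-term safety profile. Section 9.9 does not list this among the limitations.

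**Working it through.** **Inputs.** Constant recruitment over R = 4 years and a stated mean participation of about 4.5 years (section 9.5). Study duration 6 years (section 9.1.1). First visit of the first patient 17 May 2013, first visit of the last patient 17 May 2017, last visit of the last patient 29 June 2019 (section 4.10). End-of-study visit within 3 months of termination (section 6). Minimum of 30 patients (section 9.5). Last fixed antibody sample at 1 year (section 9.3.3.2). Early withdrawal is ignored.

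**Step 1: the plan's own figure.** With uniform accrual over R years and a study end T years after the first visit, mean participation is m = T − R/2. Four-year accrual gives 6 − 4/2 = 4.0 years. The stated 4.5 years is not reproduced with R = 4, but it is with R = 3: 6 − 3/2 = 4.5. Both are carried forward.

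**Step 2: follow-up after the last fixed sample.** With R = 4 and T = 6 every patient has at least 2 years of planned participation, so each contributes 1 year up to the last fixed sample. The share afterwards is (m − 1)/m.

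| R (years) | T (years) | m (years) | Share after year 1 | Person-years in 30 patients: total / after year 1 |
|---|---|---|---|---|
| 4 | 6 | 4.00 | 75% | 120 / 90 |
| 4 | 6.116 (planned last visit) | 4.116 | 76% | 123.5 / 93.5 |
| 4 | 6.25 (visit within 3 months) | 4.25 | 76% | 127.5 / 97.5 |
| 3 | 6 (matches the stated 4.5) | 4.50 | 78% | 135 / 105 |

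For single patients the share is (2 − 1)/2 = 50% for the last one recruited and (6 − 1)/6 = 83% for the first.

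**Step 3: what this implies for detection (illustration, assumed inputs).** The protocol gives neither an antibody rate nor a late-sampling rate. Let q be the share of patients sampled late. Assume that both fixed samples are taken in everyone, that antibodies persist until sampled, and that late sampling follows onset and is unrelated to antibody status. The figures are ceilings for antibodies that give no clinical or activity signal.

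- *Constant onset rate of 2% per year (assumed), participation spread evenly from 2 to 6 years.* Onset by year 1 is 1 − exp(−0.02) = 0.0198. Onset over full participation averages 0.0766. The ceiling on the share detected is [0.0198 + q(0.0766 − 0.0198)]/0.0766: 26% at q = 0, 44% at q = 0.25, 63% at q = 0.5 and 100% at q = 1.
- *80% of onsets in year 1 (assumed).* The ceiling is 0.80 + 0.20q: 80%, 85%, 90% and 100% at the same values of q.

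The possible shortfall therefore runs from nothing to about three quarters, depending on two quantities that the protocol does not state. The follow-up share in step 2 depends on neither.

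**The case against.** **Later sampling is allowed and encouraged.** This stands. Section 9.3 encourages samples at all visit types without requiring a symptom, and section 9.3.3.2 supports routine samples, supplies kits and has the sponsor pay for central assays. The prompt also includes low FXIII activity, not only clinical failure. A reader might infer that antibodies arising after year 1 will normally go undetected, or that a non-neutralising antibody prompts nothing. The protocol says neither, and its encouragement to sample works against both. What remains is that encouragement is not a schedule: late detection of silent antibodies cannot exceed the physician-selected share sampled late.

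**The 75% is not a loss.** This also stands. A reader might take it as the proportion of antibodies missed. It is follow-up time. Antibodies that cause lack of effect should prompt a sample, and routine samples may find others.

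**No 6-year incidence is specified.** Section 9.7.2.1 plans counts and percentages, and the 6-year window belongs to the whole composite. True, but section 8.1.1 names incidence as the aim, so the percentage invites that reading.

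**The listings already allow a split.** Onset dates are to be listed, and sampling times are to be recorded. Late positives can thus be separated, but nothing in section 9.7.2.1 asks for the number of patients sampled late, without which they have no denominator. An analysis plan not seen here could add the split, but it cannot recover samples never drawn.

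**The non-interventional design limits sampling.** Section 9.3 ties the two fixed samples to an FDA request and to countries where they are possible. That explains the gap and argues against demanding more blood draws. It does not argue against describing the data as they are.

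**Conclusion.** The concern holds as a mismatch between the summary period and the fixed sampling period for one of four primary-endpoint components. As planned, the percentage of patients with antibodies over full participation will tend to be low for late antibodies without loss of effect or low FXIII activity, by an amount that cannot be derived from the protocol. About 75% to 76% of follow-up lies after the last fixed sample with 4-year uniform accrual, and 78% on the stated mean of 4.5 years. For 30 patients that is about 90 to 105 person-years.

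These figures assume uniform accrual and no early withdrawal. They also treat the first year as covered in everyone, although coverage there means two time points in consenting patients in permitting countries. The conclusion does not rest on any assumed antibody rate. It is not a finding that late antibodies go unsought, nor that three quarters of antibodies are missed. It is a low-cost improvement in reporting that changes what may be concluded.

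**What to change.** In section 9.7.2.1, for the antibody component:

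1. Report occurrence from Visit 1 to year 1 among patients with samples at both times.
2. Report later positives separately, labelled *from unscheduled samples*, with the number of patients sampled after year 1 as denominator. A label such as *clinically triggered* would be wrong, because routine samples are included.
3. State that the full-participation percentage is not a 6-year antibody incidence.

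Section 9.7.2 needs a short exception, since it bases all presentations on the Full Analysis Set.

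**Cost.** A few sentences and one extra table, with no added blood draws. The downside is that the antibody claim then covers a shorter period and fewer patients.

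**Optional, for the sponsor to weigh against the non-interventional limits.** An antibody sample at visit 3 for consenting patients in permitting countries. This would cost about 2 mL of blood and one central assay per patient at a visit already held, plus a protocol amendment with ethics review. It needs new wording in the flow-chart footnote and in sections 9.3, 9.3.1.3 and 9.3.3.2. Replacing footnote 3 by footnote 4 at visit 3 would schedule nothing, because footnote 4 names only Visit 1 and the 1-year visit. A single late sample could still miss transient antibodies.
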